8. SAMPLE SIZE AND DATA ANALYSIS

8.1. Determination of Sample Size

Approximately 68 healthy subjects (at least 30% for each sex) will be randomized into 2 groups (Group 1 and 2) with 34 subjects in each. Group 2 consists of 2 sub-groups (Group 2A and 2B) and each sub-group will be randomized with 17 subjects.

Sample Size for Primary Analysis:

A sample size of 28 evaluable subjects per treatment group will provide more than 94.4% power to exclude that CBP-307 causes more than 10-msec QTc effect at clinically relevant plasma levels, as shown by the upper bound of the 2-sided 90% confidence interval (CI) of the model-predicted QT effect ($\Delta\Delta QTcF$) at the observed geometric mean C_{max} of CBP-307 in the study. This power is estimated approximately using a 2-sample t-test. The calculation assumes a 1-sided 5% significance level, an underlying effect of CBP-307 of 3 msec and a standard deviation (SD) of the $\Delta QTcF$ of 8 msec for both CBP-307 and placebo treatment groups. Note that this calculation is conservative, since it does not take into account any gain in precision due to the use of all data of each subject with the help of a linear mixed-effects model. The concentration-QTc analysis method is supported by Darpo et al 2015³ and Ferber et al, 2015,⁴ and consistent with the experiences from 25 recent TQT studies.

Sample Size Considerations for Assay Sensitivity:

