If the upper bound of the 2-sided 90% CI of the predicted QTc effect of $\Delta\Delta QTcF$ at the observed geometric mean C_{max} on Days 6 and 15 as well as clinically relevant plasma levels is below 10 msec (ie, the upper bound of the 2-sided 90% CI at the geometric mean $C_{max} < 10$ msec), it can be concluded that CBP-307 does not cause clinically concerning QT prolongation within the observed plasma concentration ranges.

Investigation of Hysteresis

Hysteresis will be assessed based on joint graphical displays of the least squares (LS) mean $\Delta\Delta QTcF$ for each postbaseline timepoint and the mean concentration of CBP-307 at the same timepoints. In addition, hysteresis plots will be given for LS mean $\Delta\Delta QTcF$ and the mean concentrations. If a QT effect ($\Delta\Delta QTcF$) > 10 msec cannot be excluded from the by-timepoint analysis in the active dose groups on Days 6 and 15; and the mean peak $\Delta\Delta QTcF$ effect is observed at the same timepoint in the by-timepoint analysis in the active dose groups on Days 6 and 15; and if the difference (delay) between the time to reach the peak QTc effect ($\Delta\Delta QTcF$) and peak plasma concentration (t_{max}) in the plot ($\Delta\Delta QTcF$ versus CBP-307) of more than 1 hour is observed in a consistent way for the active dose groups on Days 6 and 15, other concentration-QTc models, such as a model with an effect compartment, may be explored. With the provision stated above, hysteresis will be assumed if this curve shows a counterclockwise loop. A significant treatment effect-specific intercept may also be indicative of hysteresis or model misspecification, if it cannot be explained by a nonlinear relationship.

Appropriateness of a Linear Model

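### The negative-QT rule is in effect tested at the geometric mean Cmax, but its conclusion covers the whole observed concentration range

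*Protocol*

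**What the plan says.** Protocol Section 8.3, under Criteria for Negative QT Assessment, asks for an upper 90% bound below 10 msec at the observed geometric mean Cmax on Days 6 and 15, and also at plasma levels it calls clinically relevant. It gives those levels no value. A bracketed restatement then reduces the condition to "the upper bound of the 2-sided 90% CI at the geometric mean" Cmax. If the condition is met, "it can be concluded that CBP-307 does not cause clinically concerning QT prolongation within the observed plasma concentration ranges".

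The preceding paragraphs of Section 8.3 specify the prediction (slope times concentration plus a treatment-specific intercept) and its interval at the geometric mean Cmax of each of the two days, and at no other concentration.

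Section 8.1 uses the same test point. The study is powered to exclude a "more than 10-msec QTc effect at clinically relevant plasma levels, as shown by the upper bound of the 2-sided 90% confidence interval" of the model prediction at the observed geometric mean Cmax. There too, exclusion at clinically relevant levels is treated as shown by the bound at that one concentration.

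**The concern.** The condition is checked at one concentration per day, while the conclusion covers every observed concentration. Individual Cmax values scatter around the geometric mean, and about half lie above it. If the slope is positive, the predicted effect rises with concentration, and its standard error may rise too. A bound below 10 msec at the geometric mean therefore does not imply a bound below 10 msec at the top of the range.

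The study could follow its rule exactly and still declare concentrations clear at which its own model does not exclude 10 msec. The highest concentration cleared is a central result here, because Section 3.3 rules out testing substantial multiples of the anticipated maximum therapeutic exposure.

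**Working it through.** **Inputs.** From Section 8.1: "A sample size of 28 evaluable subjects per treatment group will provide more than 94.4% power"; "The calculation assumes a 1-sided 5% significance level", "an underlying effect of CBP-307 of 3 msec" and an SD "of 8 msec for both CBP-307 and placebo treatment groups"; and "This power is estimated approximately using a 2-sample t-test". From Section 8.3: the 10 msec threshold and a prediction linear in concentration. From Tables 1 and 2: the spread of Cmax. Table 1 gives standard errors of the mean, so SD = SEM × √n.

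**1. The plan's own figure.** SE = 8 × √(2/28) = 2.138 msec. With 54 degrees of freedom, t(0.95) = 1.674. The margin is 10 − 3 = 7 msec. The noncentral t gives 94.38% power, which agrees with the stated 94.4%. This power refers to the bound at the geometric mean Cmax.

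**2. What passes at the geometric mean.** The distance from estimate to upper bound is 1.674 × 2.138 = 3.58 msec. An estimate passes if it is below 10 − 3.58 = 6.42 msec. An estimate of 3 msec has an upper bound of 6.58 msec.

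**3. How far the observed range extends above the geometric mean.** The two steady-state cells of Table 2 give CVs of 1.45/4.23 = 34% (0.15 mg, Day 28) and 0.588/6.30 = 9% (0.25 mg, Day 28). The 0.5 mg fasted single dose in Table 1 gives SD 0.706 × √6 = 1.73 and CV 1.73/4.84 = 36%. Across all cells the range is 9% to 42%. Assuming lognormal Cmax, the largest value, as a multiple R of the geometric mean, is about:

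| Cmax CV | largest of 34 randomized | largest of 28 evaluable |
|---|---|---|
| 34% | 2.0 (median 1.97) | 1.92 |
| 9% | 1.21 | 1.20 |

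**4. Effects that pass but are not cleared at the top.** Assume a zero intercept and the same SE at every concentration. The bound at the largest Cmax is R × e + 3.58, where e is the estimate at the geometric mean. It exceeds 10 when e > 6.42/R.
- CV 34%: 6.42/2.0 = 3.2 msec (6.42/1.92 = 3.3 with 28 subjects).
- CV 9%: 6.42/1.21 = 5.3 msec.

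Estimates between these values and 6.42 msec satisfy the rule but leave 10 msec unexcluded at the top of the range.

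**5. Sensitivity to the SE assumption, at an estimate of 3 msec and 28 subjects.** If the SE grows in proportion to concentration, the whole bound scales and reaches 10 msec at 10/6.58 = 1.52 times the geometric mean. At the largest Cmax it is then about 12.7 msec (CV 34%) or 7.9 msec (CV 9%). If the SE is constant, the bound at CV 34% is 1.92 × 3 + 3.58 = 9.3 msec, which is below 10. With a flat slope it stays at 6.58 msec.

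**6. Chance of supporting a full-range claim when the true effect at the geometric mean is 3 msec.** A normal approximation with 28 subjects and the planning SE gives:
- CV 34%, constant SE: the estimate must be below 6.42/1.92 = 3.34. Φ((3.34 − 3)/2.138) = Φ(0.16) = 56%.
- CV 34%, proportional SE: the estimate must be below 10/1.92 − 3.58 = 1.63. Φ(−0.64) = 26%; simulation gives 27%.
- CV 9%, constant SE: the estimate must be below 6.42/1.20 = 5.35. Φ(1.10) = 86%.
- CV 9%, proportional SE: simulation gives about 80%.

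If the mixed model halved the SE, the proportional-SE figures would rise to about 62% (CV 34%) and nearly 100% (CV 9%).

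**The case against.** **The rule names a second condition.** It would be too strong to say without qualification that the text tests only the geometric mean, because it also mentions clinically relevant levels, and a value for them could sit in an analysis plan not shown here. However, the restatement in Section 8.3 and the power statement in Section 8.1 both reduce that condition to the geometric mean Cmax. Even read literally, it does not reach the highest observed concentration.

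**Worst-case exposure is tested.** A reader might infer that the exposures listed in Section 1.4 (CYP3A4 inhibition, liver disease, excess dosing) go untested. The protocol does not support that. The supratherapeutic dose is meant to mimic them, and the bound is required at its Day 15 geometric mean. What remains untested is the upper tail of individual concentrations above that mean.

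**The size depends on assumptions.** This objection stands. The model estimates an intercept, and with a non-zero intercept the effect does not scale with concentration. The Cmax spread at 0.5 mg steady state is not given, and the two steady-state CVs differ widely. At CV 9% and an estimate of 3 msec there is no gap. At CV 34% the gap appears at 3 msec only if the SE also grows.

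**Upper-range behavior will be visible.** Section 8.3 requires a decile plot with 90% intervals and the model line. That helps readers, but the plot checks fit and does not limit the conclusion.

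**A full-range criterion would rest on one extreme value.** This is fair, and it is a reason to narrow the claim while leaving the test as it is.

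**Conclusion.** The mismatch is real and lies in the protocol's own decision sentence: the test is made at the geometric mean Cmax, and the conclusion runs over all observed concentrations. With planning SE 2.138 msec, zero intercept, constant SE and lognormal Cmax, estimates from about 3.2 msec (CV 34%) or about 5.3 msec (CV 9%) up to 6.4 msec would pass while the bound at the largest observed Cmax exceeds 10 msec. This shows that the rule can overreach. It does not show how often, because slope, intercept, SE and Cmax spread are not given.

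Two stronger inferences fail. The sample size is not wrong: its power reproduces for the concentration it addresses. Nor is it established that a true effect at the planned 3 msec would usually leave the top of the range uncleared, since that depends on the spread and on how the SE behaves. The model, threshold and test concentration are unaffected; the defect is the scope of the conclusion.

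**What to change.** Keep the test at the geometric mean Cmax on Days 6 and 15, with its 94.4% power, and change the conclusion in one of two ways:
- limit it to concentrations up to the Day 15 geometric mean Cmax; or
- state that an effect above 10 msec is excluded up to the highest observed concentration at which the model's upper 90% bound is still below 10 msec, and report that concentration as a multiple of the Day 15 geometric mean Cmax.

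Claim the full observed range only if the bound at the highest observed concentration is below 10 msec. Also give the clinically relevant levels a value, or delete the phrase.

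The change needs one reworded sentence and, for the second option, further predictions from the same fitted model. It needs no new data, subjects or visits. The downside is a possibly narrower claim: with a Cmax CV near 34%, the planning SE and a true effect of 3 msec, a full-range claim would succeed in roughly 27% to 56% of trials, depending on how the SE behaves, against 94.4% for the existing test.

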8.4. Pharmacokinetic Analyses

The analyses will be carried out on the PK analysis population. All PK parameters will be presented by listings and descriptive summary statistics (mean, SD, median, minimum, maximum geometric mean, and geometric coefficient of variation) separately by group. Individual and mean plasma CBP-307 and moxifloxacin concentration versus time data will be tabulated and plotted by dose level. Graphical displays of PK data may be provided as well.

For each subject, the following PK parameters will be calculated, whenever possible, based on the plasma concentration for CBP-307 and moxifloxacin, according to the model independent approach:

- C_{\max}
- t_{\max}
- AUC_{0-24}
- AUC_{inf}
- apparent terminal elimination rate constant (λ_Z)
- $t_{1/2}$
- apparent total clearance (CL/F)
- apparent volume of distribution during the terminal phase (V_z/F)

Pharmacokinetic calculations will be performed, if appropriate, using commercial software such as Phoenix® WinNonlin® (Version 8.1 or higher).

Other parameters may be added as appropriate.

Pharmacokinetic analysis will use actual times as recorded on the eCRF. Other data handling procedures will be detailed in the Statistical Analysis Plan.

8.5. Safety Analysis

All AEs will be listed and treatment-emergent AEs will be summarized using the descriptive methodology. Each AE will be coded using the Medical Dictionary for Regulatory Activities. Observed values for clinical laboratory test data, 12-lead ECGs, vital signs, and physical examination findings will be listed.

8.6. Interim Analysis

No interim analyses are planned for this study.

10. APPENDICES

Appendix 1: Adverse Event Reporting

Definitions

An AE is any untoward medical occurrence in a subject or clinical investigation subject administered a pharmaceutical product, which does not necessarily have a causal relationship with this treatment. An AE can therefore be any unfavorable and/or unintended sign (including a clinically significant abnormal laboratory finding), symptom, or disease temporally associated with the use of a study treatment, whether or not related to the study treatment. This includes any newly occurring event or previous condition that had increased in severity or frequency since the administration of study medication.

Examples of AEs include:

- Symptoms described by the subject, or signs observed by the investigator, and
- Abnormal findings (involving clinically significant abnormal laboratory tests, ECG, etc.)
- Exacerbation of previous condition, including increased incidence and/or severity.

Note: Regarding decreased lymphocyte count in peripheral blood in this study, please report them as follows:

- Since a decreased lymphocyte count in peripheral blood is due to the mechanism of action of the drug, it is not to be reported as an AE. However, clinical diagnosis related to a decreased lymphocyte count in peripheral blood indicates AE reporting (if no diagnosis is available, it is required to report related clinical symptoms or signs).

The investigator is to report all directly observed AEs and all AEs spontaneously reported by the study subject. In addition, each study subject will be questioned about AEs. All AEs will be recorded in the medical records and eCRFs. The investigator (or designee) is to record in detail any AE that occurred to the subject, including: AE diagnosis whenever possible, or signs, symptoms, the start date and time of occurrence, the stop date and time of occurrence, seriousness (ie, whether it is an SAE), severity of AEs, causality assessment, actions taken on the investigational product, other actions (eg, medications/treatments given), and outcomes of AEs.

Assessment of Severity

The investigator will be asked to provide an assessment of the severity of the AE using the following categories:

- **Mild:** Usually transient and may require only minimal treatment or therapeutic intervention. The event does not generally interfere with usual activities of daily living.
- **Moderate:** Usually alleviated with additional specific therapeutic intervention. The event interferes with usual activities of daily living, causing discomfort but poses no significant or permanent risk of harm to the subject.

- **Severe:** Interrupts usual activities of daily living, or significantly affects clinical status, or may require intensive therapeutic intervention.

Relationship to Study Treatment

The investigator (or designee) will make a determination of the relationship of the AE to the study treatment using a 4-category system according to the following guidelines:

- **Not Related:** The AE is definitely caused by the subject's clinical state or the study procedure/conditions.
- **Unlikely Related:** The temporal association between the AE and the drug is such that the drug is not likely to have any reasonable association with the AE.
- **Possibly Related:** The AE follows a reasonable temporal sequence from the time of drug administration but could have been produced by the subject's clinical state or the study procedures/conditions.
- **Related:** The AE follows a reasonable temporal sequence from the administration of the drug, abates upon discontinuation of the drug, follows a known or hypothesized cause-effect relationship, and (if appropriate) reappears when the drug is reintroduced.

Follow-up of Adverse Events

Every reasonable effort will be made to follow up with subjects who have AEs. Any subject who has an ongoing AE that is possibly related or related to the IMP or study procedures at the follow-up visit will be followed up, where possible, until resolution or until the unresolved AE is judged by the investigator (or designee) to have stabilized. This will be completed at the investigator's (or designee's) discretion. Any subject who has an ongoing AE that is not related or unlikely related to the IMP or study procedures at the follow-up visit can be closed out as ongoing at the investigator's discretion.

Adverse Drug Reactions

All noxious and unintended responses to an IMP (ie, where a causal relationship between an IMP and an AE is at least a reasonable possibility) related to any dose should be considered adverse drug reactions.

For marketed medicinal products, a response to a drug that is noxious and unintended and which occurs at doses normally used in man for prophylaxis, diagnosis, or therapy of diseases or modification of physiological function is to be considered an adverse drug reaction.

An unexpected adverse drug reaction is defined as an adverse reaction, the nature or severity of which is not consistent with the applicable product information (eg, IB for an unapproved IMP).

Serious Adverse Events

All SAEs will be collected after subjects sign the informed consent form and throughout the entire study, ie, until the end-of-study as specified in the protocol (or at early termination).

An SAE is defined as any untoward medical occurrence that at any dose either:

- results in death
- is life-threatening
- requires inpatient hospitalization or prolongation of existing hospitalization
- results in persistent or significant disability/incapacity (disability is defined as a substantial disruption of a person's ability to conduct normal life functions)
- results in a congenital anomaly/birth defect
- results in an important medical event (see below).

Important medical events that may not result in death, be life-threatening, or require hospitalization may be considered SAEs when, based upon appropriate medical judgment, they may jeopardize the subject and may require medical or surgical intervention to prevent one of the outcomes listed in this definition.

Instances of death or congenital abnormality, if brought to the attention of the investigator at any time after cessation of the study treatment and considered by the investigator to be possibly related to the study treatment, will be reported to the sponsor (or designee).

Definition of Life-threatening

An AE is life-threatening if the subject was at immediate risk of death from the event as it occurred (ie, does not include a reaction that might have caused death if it had occurred in a more serious form). For instance, drug-induced hepatitis that resolved without evidence of hepatic failure would not be considered life-threatening even though drug-induced hepatitis can be fatal.

Definition of Hospitalization

Adverse events requiring hospitalization should be considered serious. In general, hospitalization signifies that the subject has been detained (usually involving an overnight stay) at the hospital or emergency ward for observation and/or treatment that would not have been appropriate at the study site. When in doubt as to whether hospitalization occurred or was necessary, the AE should be considered as serious.

Hospitalization for elective surgery or routine clinical procedures, which are not the result of an AE, need not be considered AEs and should be recorded on a clinical assessment form and added to the eCRF. If anything untoward is reported during the procedure, this must be reported as an AE and either 'serious' or 'nonserious' attributed according to the usual criteria.

Serious Adverse Event Reporting

The investigator will complete an SAE report form and forward it by facsimile or email to Labcorp Drug Safety and the sponsor immediately (within 24 hours) upon becoming aware of an SAE.

All SAEs must be reported immediately (within 24 hours of discovery) to:
[contact] (AUS) or [name] (US)

SAE Reporting email: [contact] (preferred method)

Labcorp Safety SAE Reporting Fax Numbers: [name] or [name] (toll free) in Australia and [name] (toll free) in the US

The responsibilities of Labcorp Drug Safety include the following:

- Prepare an AE reporting plan prior to the start of the study. Where this plan differs from the applicable study site standard operating procedure on SAE reporting, the safety management plan will always take precedence.
- Receive and review SAE report forms from the study site and inform the sponsor of the SAE within 1 working day of the initial notification to Labcorp Drug Safety who will delete any information from the SAE report forms that may identify the subject.
- Write case narratives and enter the case into Labcorp's safety database as defined in the AE reporting plan.
- Produce appropriate reports of all suspected unexpected serious adverse reactions and forward them to the IRB/EC, Medicines and Healthcare Products Regulatory Agency, FDA, principal investigator, and the sponsor within the timeframes stipulated in the Clinical Trials Directive Guideline (ENTR/CT 3).

The responsibility for reporting SAEs will be transferred to the sponsor 28 days after the end of the study.

For SAEs, the active reporting period to sponsor or its designated representative begins from the time that the subject provides informed consent through to the last subject visit.

Nonserious AEs should be collected from the time the subject has taken the placebo dose on Day -1 through the last subject visit. If AEs that occur in the screening prior to the placebo administration to all subjects on Day -1 are considered to be related to the study procedure, they should be also collected.

The investigator is to report all directly observed AEs and all AEs spontaneously reported by the study subject. In addition, each study subject will be questioned about AEs.

Each AE is to be assessed to determine if it meets the criteria for SAEs. If an SAE occurs, the sponsor should be notified within 24 hours of investigator awareness of the event. This time frame also applies to additional new information (follow-up) on previously forwarded SAE reports as well as to the initial and follow-up reporting of exposure during pregnancy.

In the rare event that the investigator does not become aware of the occurrence of an SAE immediately (eg, if an outpatient study subject initially seeks treatment elsewhere), the investigator is to report the event within 24 hours after learning of it and document the time of his or her first awareness of the AE.

For all SAEs, the investigator is obligated to pursue and provide information to the sponsor in accordance with the time frames for reporting as specified above. In addition, an investigator

may be requested by the sponsor to obtain specific additional follow-up information in an expedited fashion. This information collected for SAEs is more detailed than that captured on the AE eCRF. In general, this will include a description of the AE in sufficient detail to allow for a complete medical assessment of the case and independent determination of possible causality. Information on other possible causes of the event, such as concomitant medications, vaccines, and/or illnesses, must be provided. In the case of a subject death, a summary of available autopsy findings must be submitted as soon as possible to the sponsor or its designated representative.

Pregnancy

Pregnancy (maternal or paternal exposure to study treatment) does not meet the definition of an AE. However, to fulfill regulatory requirements any pregnancy should be reported following the SAE process to collect data on the outcome for both mother and fetus.

If the female subject becomes pregnant during the clinical trial and has not yet been dosed with study treatment, she must be withdrawn from the study. If the female subject becomes pregnant during the clinical trial and has been dosed, she must discontinue treatment immediately but may remain on study for safety evaluations. If the partner of a male subject becomes pregnant during the clinical trial, the subject can continue the clinical trial.

For pregnancy of female subjects or partners of the male subjects during this study, investigators should report to the sponsor or designee in a pregnancy report form within 24 hours after investigator awareness and report to the IRB/EC in time as per local requirement.

The investigator will follow up on pregnancy outcomes, until not less than 12 months after birth, unless otherwise justified, and will report the outcome to the sponsor and IRB/EC.

If any adverse pregnancy outcome (eg, the outcome of the pregnancy is stillbirth, spontaneous abortion, or fetal malformations), it should be considered as an SAE and be reported in accordance with SAE reporting requirements.

